4.1 Overall Design

This is a phase 1b study assessing safety, tolerability, PK, pharmacodynamics, and efficacy of AMG 330 administered as clV infusion in combination with pembrolizumab in adult subjects with R/R AML.

The study is a non-randomized study and will consist of 2 sequential dosing cohorts. Both cohorts will include AMG 330 and pembrolizumab with the difference being the initiation date for pembrolizumab treatment.

This study will use a staggered enrollment approach. Subject enrollment will start with cohort 1 ([Section 4.1.1](#)). The first subject dosed in cohort 1 will serve as the sentinel subject. Subsequent subjects dosed in cohort 1 will start AMG 330 (█ µg/day) administration once sentinel subject has cleared the study day 21 dose (AMG 330 monotherapy at █ µg/day). Per sponsor determination, if the sentinel subject does not experience a dose-limiting toxicity (DLT) on days 15 to 21 after pembrolizumab is administered, the other subjects in cohort 1 will be allowed to continue the planned treatment schedule. If the sentinel subject experiences a DLT during days 15 to 21, the dose level review team (DLRT) will discuss the case and the decision will be made by the sponsor based on clinical assessments of the adverse event and potential decisions by the sponsor may include stopping AMG 330 and/or pembrolizumab, dose de-escalation of AMG 330, or continuing therapy at full dose. Investigators and sponsor will meet after all subjects in cohort 1 have completed study day 28 (ie, AMG 330 █ µg/day dose level in combination with pembrolizumab) to assess the safety profile. If pre-specified safety criteria are met (≤ 3 out of 10 treated subjects in cohort 1 experienced DLT by day 28), subjects enrolled in cohort 2 ([Section 4.1.2](#)) may proceed with the treatment schedule. Similar to cohort 1, the first subject dosed in cohort 2 will serve as the sentinel subject. Per sponsor determination, if the sentinel subject does not

experience a DLT during the first 7 days, the other subjects in cohort 2 will be allowed to continue the planned treatment schedule.

Safety data will be continuously monitored throughout the whole treatment period. Sponsor in consultation with investigators may reconvene to make appropriate safety measures and adjustments as needed.

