6.2 Dose Modification

6.2.1 Dose-cohort Study Escalation/De-escalation and Stopping Rules, Dose-Limiting Toxicities (DLTs)

Step Dose Level Determination

A decision to proceed with the next step dose of AMG 330 for each subject in cohorts 1 and 2 will be based on investigator's assessment of safety and upon approval by Sponsor.

In cohort 1, a sentinel subject will be treated first. The minimal interval between treatment start for the sentinel subject and other subjects in the cohort is 21 days. If the sentinel subject has not experienced a DLT by day 14 at █ µg/day AMG 330, he/she will proceed with 200 mg pembrolizumab on day 15 and remain at an AMG 330 dose level of █ µg/day for 7 days (until day 21). If the sentinel subject experiences a DLT during the first 7 days of treatment with AMG 330 at █ µg/day, this subject will be replaced, but the DLT will still be counted towards the study stopping rules. If the sentinel subject does not experience a DLT before or on day 21, the next subjects in the cohort may initiate dosing. If a sentinel subject experiences a DLT, the sponsor will issue a decision based on the evaluation of clinical significance of the adverse event by the DLRT and potential decisions by the sponsor may include stopping AMG 330 and/or pembrolizumab, dose de-escalation of AMG 330, or continuing therapy at full dose.

Cohort 2 will be initiated only after all subjects in cohort 1 completed study day 28 (ie, AMG 330 █ µg/day dose level in combination with pembrolizumab for 7 days), and if the rate of DLT is ≤ 3 out of 10 subjects. After receiving the DLRT recommendation, sponsor will render a final decision and will issue a written notification of the decision to investigators. Further information on dose level review meetings (DLRMs) is provided in [Section 11.3](#).

Individual Stopping Rules

Dosing for an individual will be stopped for any occurrence of a DLT. The event will be reviewed by the investigator and Sponsor for evidence of relationship to treatment and

clinical or medical significance to decide whether dosing may be resumed for the individual and any modifications to the dosing, if appropriate.

Dose Limiting Toxicities

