A DLT will be defined as any of the events described below occurring in a subject during the DLT window, unless clearly attributable to causes other than investigational product. The DLT window will start on day 1 and last for the duration of cycle 1. The CTCAE v5 will be used to assess toxicities/adverse events with the exception of CRS (see [Table 6-5](#) for grading of CRS).

DLT Evaluation

To be DLT evaluable, subjects must meet 1 of the following criteria during DLT evaluation period (cycle 1 day 1 to cycle 1 end of infusion):

- The subject experienced a DLT; OR
- The subject has received at least 70% of planned cumulative dose of AMG 330 and has not missed more than 1 dose of pembrolizumab; OR
- The subject did not experience a DLT and completed the DLT evaluation period

Events listed below are to be considered as DLTs and exceptions when occurring in a subject during the DLT window unless clearly attributable to causes other than AMG 330 and pembrolizumab treatment:

- Any treatment-related death.
- Grade 4 neutropenia lasting \geq 4 weeks from last day of cycle in absence of evidence of active AML. Note: grade 4 neutropenia maybe assessed retrospectively and outside of the DLT window
- Grade 3–4 non-hematologic toxicity not clearly resulting from the underlying leukemia EXCEPT:
 - Grade 3 fatigue, asthenia, fever, anorexia, or constipation
 - Grade 3 nausea, vomiting or diarrhea not requiring tube feeding, total parenteral nutrition, or requiring or prolonging hospitalization
 - Infection, bleeding, or other expected direct complication of cytopenias due to active underlying leukemia
 - Grade 3 infusion reaction, unless attributed to pembrolizumab, if successfully managed and which resolves within 72 hours
 - Grade 3 rash or pruritus
 - Grade 3 or 4 tumor lysis syndrome if it is successfully managed clinically and resolves within 7 days without end-organ damage.

Approved

- Grade 3 or 4 isolated analyte abnormalities (ie, those occurring without clinical consequence) that resolve, with or without intervention, to < grade 2 levels in < 72 hours will not be considered DLT.
- Grade 3 or 4 asymptomatic enzyme elevations including aspartate aminotransferase (AST), alanine aminotransferase (ALT) (without bilirubin elevation), gamma glutamyl transferase that resolve, with or without intervention, to ≤ grade 2 within 7 days will not be considered a DLT, unless attributed to pembrolizumab.

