- Isolated grade 3 elevation of amylase or lipase not associated with clinical or radiological evidence of pancreatitis
- Grade 3 endocrinopathy that is well controlled by hormone replacement
- CRS meeting any of the criteria listed below:
 - Grade 2 CRS that does not resolve, with or without intervention to grade 1 within 7 days will be considered a DLT
 - Grade 3 CRS that does not resolve, with or without intervention to ≤ grade 2 within 5 days, will be considered a DLT
 - Any grade 4 CRS
- Any grade 5 toxicity
- Receive less than 70% of the planned cumulative dose of AMG 330 or miss more than 1 dose of pembrolizumab during the first cycle due to investigational product(s) related toxicity that does not meet the DLT criteria listed above

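### Cohort 2 has a sentinel but no explicit start hold for its other subjects, and the day 7 check can pass while grade 2 CRS from the day 4 step is still open

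*Protocol*

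**What the plan says.** **Study-wide.** Protocol Section 4.1 states: "This study will use a staggered enrollment approach".

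**Cohort 1.** Section 4.1 lets later subjects begin AMG 330 only once the sentinel has cleared day 21. Section 6.2.1 gives the interval, "The minimal interval between treatment start for the sentinel subject and other subjects in the cohort is 21 days", and the release, "If the sentinel subject does not experience a DLT before or on day 21, the next subjects in the cohort may initiate dosing". Both sentences stand in a paragraph that opens by naming cohort 1.

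**Cohort 2.** Section 4.1 introduces the sentinel as resembling that of cohort 1. The only rule for the other subjects is that, per sponsor determination, should the sentinel not "experience a DLT during the first 7 days, the other subjects in cohort 2 will be allowed to continue the planned treatment schedule". The synopsis (Section 1.1) and SAP Section 3.1 say the same. Section 4.1.2 adds no interval, and Section 6.2.1 controls only when the cohort opens.

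**CRS as a DLT (Section 6.2.1).** Two criteria run on a clock: "Grade 2 CRS that does not resolve, with or without intervention to grade 1 within 7 days will be considered a DLT", and "Grade 3 CRS that does not resolve, with or without intervention to ≤ grade 2 within 5 days, will be considered a DLT". By contrast, CRS of grade 4 is a DLT at once. A separate general criterion makes a DLT of grade 3–4 non-hematologic toxicity "not clearly resulting from the underlying leukemia EXCEPT" for a list of exceptions, and CRS is not on that list.

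**The concern.** The protocol treats *start* and *continue* as different things. Cohort 1 has a rule for each, and only the *continue* sentence is carried over to cohort 2. A site that follows the text could dose a second cohort 2 subject during the sentinel's first week.

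Cohort 2 is the first use of both drugs from day 1. Cohort 1 subjects have 14 days of AMG 330 alone first, and the mitigation in Section 2.3 that introduces pembrolizumab 7 days after an AMG 330 step is specific to cohort 1. Section 2.3 also says that blocking PD-1 could lead to higher grades of CRS. Stopping at day 7 can prevent the day 8 step in other subjects, but it cannot withdraw pembrolizumab that they have already received.

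The check itself is also exposed. It looks only for a DLT, and some CRS cannot be classified as a DLT or not until after day 7.

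**Working it through.** **The plan's own figure.** The stated 82% chance of at least one DLT in 6 subjects at a true rate of 25% reproduces: 1 − 0.75^6 = 0.822. It does not bear on this point, which rests on wording and day counts.

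**Step 1. The two cohorts side by side (readable text).**

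| Rule | Cohort 1 | Cohort 2 |
|---|---|---|
| When other subjects may start | After sentinel clears day 21 (4.1, 6.2.1) | Not stated |
| Minimum interval from sentinel's start | 21 days (6.2.1) | Not stated |
| When other subjects may continue | No sentinel DLT on days 15–21 (4.1) | No sentinel DLT in first 7 days (4.1) |
| Action on a sentinel DLT | Dose level review team (DLRT) evaluates, sponsor decides (4.1, 6.2.1) | Only the 6.2.1 sentence "If a sentinel subject experiences a DLT, the sponsor will issue a decision based on the evaluation of clinical significance", general in wording but placed in the cohort 1 paragraph |

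**Step 2. When the CRS criteria are decided.** Inputs: Table 4-3 (AMG 330 steps on days 1–3, 4–7 and 8–14; pembrolizumab on day 1) and the limits of 7 days (grade 2) and 5 days (grade 3). Assume that the clock runs from onset on day d. Grade 2 is then decided on day d + 7 and grade 3 on day d + 5. If the onset day counts as the first day, these become d + 6 and d + 4, shown in brackets.

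| Onset day | Grade 2 decided | Grade 3 decided |
|---|---|---|
| 1 | 8 (7) | 6 (5) |
| 2 | 9 (8) | 7 (6) |
| 3 | 10 (9) | 8 (7) |
| 4 | 11 (10) | 9 (8) |
| 7 | 14 (13) | 12 (11) |

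For onset on day 4, grade 2 is decided 3–4 days after the check closes and grade 3 1–2 days after, under either count. The grade 3 overrun applies only if the CRS-specific criterion governs. Under the general grade 3–4 criterion, grade 3 CRS could count at once, and the text does not say which applies. Grade 4 has no clock.

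**Step 3. How many could start early.** With a start hold: none. Without one it depends on accrual, which the documents do not give. As an assumption only, take 1, 2 or 4 cohort 2 starts per month, a Poisson count and 30.4 days per month.

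- Mean in 7 days = rate × 7/30.4 = 0.23, 0.46, 0.92.
- Chance of at least one = 1 − exp(−mean) = 21%, 37%, 60%.
- If subjects from a 14-day screening window are also waiting (21 days in all), the means are 0.69, 1.38 and 2.76.

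**The case against.** The strongest reply is that a hold is already meant. The staggered approach is declared for the whole study, and the cohort 2 sentinel is likened to that of cohort 1. The same *continue* phrase is used in cohort 1, where a start hold plainly exists. The schema figures, to which Section 4.1.2 refers, are not shown and may carry the interval. This stands as to intent. A reader might infer that the protocol means to dose cohort 2 subjects together; the documents do not support that. What remains is that the readable text does not state the hold.

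Second, cohort 2 does not open on untested ground. At least 10 cohort 1 subjects must have been dosed through day 28, with pembrolizumab on day 15 alongside the third AMG 330 step and then the fourth (Table 4-1). The recommendation to open cohort 2 needs a unanimous vote (Section 11.3). Only same-day initiation is new. The first week uses the two lowest doses, at which Section 4.3 calls CRS rare, although on AMG 330 monotherapy experience. This stands and limits the risk.

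Third, release is per sponsor determination, each step increase needs sponsor approval, and each step carries 72 hours in hospital. The sponsor could therefore withhold release while CRS is open. True, but none of these sets a hold on another subject's first dose, and nothing tells the sponsor to wait.

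Fourth, a reader might infer that the day 7 check misses CRS DLTs generally. It does not: grade 4 counts at once, and grade 3 may. The clear overrun is persistent grade 2 CRS.

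Finally, the third step starts on day 8, after the check, and a 7-day hold does not change that. It need not: with a 7-day lead the sentinel finishes days 8–14 before the others reach day 8.

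**Conclusion.** The point holds as a gap in a written safety rule that should be closed before cohort 2 opens. It is not evidence that the design omits a stagger. Two things follow from the text as it reads:

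- Other cohort 2 subjects may receive both drugs before the sentinel completes day 7.
- A DLT-only check at day 7 can clear a sentinel whose grade 2 CRS from the day 4 step is not decidable until day 10 or 11. Grade 3 (day 8 or 9) joins it only if the CRS-specific criterion takes precedence.

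The day counts depend on the clock starting at onset; the conclusion for day 4 is the same under both ways of counting. The 21% to 60% range rests wholly on assumed accrual and should not be read as an estimate for this trial. No sample size or operating characteristic changes. Confidence is moderate, because the schema figures could not be read.

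**What to change.** Add to protocol Sections 1.1, 4.1 and 6.2.1 and to SAP Section 3.1:

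*No other cohort 2 subject will start pembrolizumab or AMG 330 until the sentinel has completed day 7 without a DLT. If the sentinel has grade 2 or higher CRS unresolved at day 7, starts wait until it resolves to grade 1 or lower or meets the DLT criteria. If the sentinel has a DLT, no further subject starts until the sponsor issues a decision after DLRT evaluation, as in cohort 1.*

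The cost is wording in four places and a 7-day delay for the other cohort 2 subjects. The delay rises to about 14 days if CRS is open at day 7 (grade 2 onset on day 7: 7 + 7 = 14). Cohort 1 already accepts 21 days. A sentinel DLT would need one unscheduled DLRT review; if held as a formal dose level review meeting, it needs a quorum of more than 50% of investigators (Section 11.3). No subjects are added.

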4.1.1 Cohort 1 Design

Cycle 1 is 77 days in duration and subsequent cycles are 57 days. Treatment will start with AMG 330 on day 1. Dexamethasone 8 mg will be given to subjects 1 hour prior to each step dose of AMG 330. AMG 330 will be administered at a starting dose of [REDACTED] µg/day for 3 days, followed by [REDACTED] µg/day for 4 days, followed by [REDACTED] µg/day for 7 days. If the subject experiences DLT during these first 7 days of treatment with AMG 330 at [REDACTED] µg/day, this subject will be replaced. If the subject has not experienced a DLT by day 14, they will receive pembrolizumab on day 15. Pembrolizumab will be administered at a dose of 200 mg (Q3W) by a 30-minute IV infusion. The subject will remain at an AMG 330 dose level of [REDACTED] µg/day for additional 7 days.

Thereafter, AMG 330 dosing will continue as per [Table 4-1](#), increasing dose levels to [REDACTED] µg/day for 7 days followed by [REDACTED] µg/day for 7 days. If the subject has not experienced a DLT at the [REDACTED] µg/day dose level of AMG 330 between days 29 to 35, they will receive pembrolizumab on day 36 and remain on the AMG 330 [REDACTED] µg/day dose for an additional 7 days. AMG 330 dosing will further increase to [REDACTED] µg/day for 7 days followed by [REDACTED] µg/day for 7 days. If the subject has not experienced a DLT at

the █ µg/day dose level of AMG 330 between days █ to █, they will receive pembrolizumab on day 57 and remain on the █ µg/day dose for additional 7 days. To complete cycle 1, a final dose level increase to █ µg/day AMG 330 for an additional 14 days will be administered.

Cycle 1 will be followed by a 1-week interval without AMG 330 administration and administration of pembrolizumab will continue non-interrupted on the Q3W schedule.

The AMG 330-infusion free interval may be extended up to 4 weeks (depending on safety, treatment response, and in case of prolonged marrow aplasia and cytopenia in aleukemic subjects) after consultation with the sponsor.

Table 4-1. Dosing for Cohort 1 (Cycle 1)

AMG 330 Dose Level (µg/day, cIV)	AMG 330 Days Administered	Pembrolizumab Days Administered (IV infusion)
█	D1-3	
	D4-7	
	D8-14, D15-21	D15
	D22-28	
	D29-35; D36-42	D36
	D43-49	
	D50-56; D57-63	D57
	D64-77	
(infusion-free period)	D78-85	D78

cIV = continuous intravenous; D = day; IV = intravenous

Cycle 2 will start with the initiation of AMG 330 administration and include the same step dose levels and duration as in cycle 1 with the exception of the █ and █ µg/day dose levels, which will be shortened from 14 days to 7 days (Table 4-2). The duration of AMG 330 step dose levels in cycle 2 and beyond can be shortened to 2 to 5 days if a subject tolerated the investigational product in cycle 1 and based on the discussion and agreement between the investigator and the sponsor. All subsequent cycles will be conducted similarly to cycle 2.

On days when pembrolizumab administration and an AMG 330 dose level increase will occur, the subject will receive dexamethasone 8 mg at the conclusion of the pembrolizumab infusion. Dexamethasone will be given 1 hour prior to increasing the AMG 330 dose. If the subject does not develop a ≥ grade 2 infusion reaction, or if the

infusion reaction is reversible after the 1-hour observation period, AMG 330 may be increased to the next dose level, as shown in [Table 4-2](#).

Table 4-2. Dosing for Cohort 1 (Cycle 2 and Beyond)

AMG 330 Dose Level (μ g/day, clV)	AMG 330 Days Administered	Pembrolizumab Days Administered (IV infusion)
	D1-3	
	D4-7	
	D8-14	
	D15-21	D15
	D22-28	
	D29-35	
	D36-42	D36
	D43-56	
(infusion period)	D57-64	D57

clV = continuous intravenous; D = day; IV = intravenous

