4.2.1 Replacement of Subjects

Ineligible subjects (ie, subjects who were exposed to AMG 330 or pembrolizumab, but post hoc were found to be ineligible) may be replaced. Subjects who do not meet the DLT evaluable criteria (see [Section 6.2.1](#)) may be replaced until at least 6 subjects become DLT evaluable in each cohort or at least 10 subjects in cohort 1 have been dosed through study day 28. If a sentinel subject in cohort 1 experiences a DLT at [REDACTED] μ g/day, [REDACTED] μ g/day or [REDACTED] μ g/day of AMG 330 during the first 14 days of monotherapy treatment in cycle 1, this subject will be defined as DLT evaluable and will not proceed

with the combination regimen. The sentinel role will be re-assigned to the next available subject.

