9.4.1 Planned Analyses

9.4.1.1 Interim Analysis and Early Stopping Guidelines

Safety data will be reviewed on an ongoing basis. A DLRM will occur when at least 10 treated subjects in cohort 1 have been dosed through study day 28 to determine if the safety profile of initial steps in cohort 1 is acceptable to begin enrollment of cohort 2 or if the study should be stopped. If 3 or more of the 10 treated subjects in cohort 1 experience a DLT by day 28, the guidance to the DLRT is to recommend not to initiate cohort 2. The stopping rule is based on having at least a posterior probability of > 70% that the DLT rate is > 20% assuming a prior distribution of Beta (0.40, 1.60). If the true DLT rate is 10%, 20%, 30%, 40%, or 50%, then the probability of stopping the study at the interim analysis is 7%, 32%, 62%, 83%, 95%, respectively.

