## 3.1.1 Cohort 1 Design

Cycle 1 is 77 days in duration and subsequent cycles are 57 days. Treatment will start with AMG 330 on day 1. Dexamethasone 8 mg will be given to subjects 1 hour prior to each step dose of AMG 330. AMG 330 will be administered at a starting dose of µg/day for 3 days, followed by µg/day for 4 days, followed by µg/day for 7 days. If the subject experiences DLT during these first 7 days of treatment with AMG 330 at µg/day, this subject will be replaced. If the subject has not experienced a DLT by day 14, they will receive pembrolizumab on day 15. Pembrolizumab will be administered at a dose of 200 mg (Q3W) by a 30-minute IV infusion. The subject will remain at an AMG 330 dose level of µg/day for additional 7 days.

Thereafter, AMG 330 dosing will continue as per Table 3-1, increasing dose levels to µg/day for 7 days followed by µg/day for 7 days. If the subject has not experienced a DLT at the µg/day dose level of AMG 330 between days 29 to 35, they will receive pembrolizumab on day 36 and remain on the AMG 330 µg/day dose for an additional 7 days. AMG 330 dosing will further increase to µg/day for 7 days followed by µg/day for 7 days. If the subject has not experienced a DLT at the µg/day dose level of AMG 330 between days 50 to 56, they will receive pembrolizumab on day 57 and remain on the µg/day dose for additional 7 days. To complete cycle 1, a final dose level increase to µg/day AMG 330 for an additional 14 days will be administered.

Cycle 1 will be followed by a 1-week interval without AMG 330 administration and administration of pembrolizumab will continue non-interrupted on the Q3W schedule. The AMG 330-infusion free interval may be extended up to 4 weeks (depending on safety, treatment response, and in case of prolonged marrow aplasia and cytopenia in aleukemic subjects) after consultation with the sponsor.

Cycle 2 will start with the initiation of AMG 330 administration and include the same step dose levels and duration as in cycle 1 with the exception of the and pg/day dose levels, which will be shortened from 14 days to 7 days (Table 3-2). The duration of AMG 330 step dose levels in cycle 2 and beyond can be shortened to 2 to 5 days if a subject tolerated the investigational product in cycle 1 and based on the discussion and agreement between the investigator and the sponsor. All subsequent cycles will be conducted similarly to cycle 2.

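### The cohort 1 interim safety rule does not say clearly whether a lead-in DLT in a replaced, non-sentinel subject stays in the count, or who makes up the denominator

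*Protocol*

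**What the plan says.** **Replacement.** Protocol 4.1.1 covers any cohort 1 subject: "If the subject experiences DLT during these first 7 days of treatment with AMG 330" at one (redacted) dose level, "this subject will be replaced". On the 4.1.1 schedule this is apparently days 8–14. SAP 3.1.1 has the same rule ("If the subject experiences DLT during these first 7 days of treatment with"). Neither says what happens to the DLT.

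**Counting.** Protocol 6.2.1 addresses the point for the sentinel only, over the same 7 days: "this subject will be replaced, but the DLT will still be counted towards the study stopping rules". No matching sentence covers other subjects.

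**Evaluability.** Protocol 4.2.1 covers a sentinel with a DLT in the first 14 days of monotherapy, at any of three dose levels: "this subject will be defined as DLT evaluable and will not proceed" to the combination. Apart from ineligible subjects, it ties replacement to subjects who are not DLT evaluable. They "may be replaced until at least 6 subjects become DLT evaluable in each cohort" or until 10 in cohort 1 have been dosed to day 28. Under 6.2.1, anyone with a DLT is evaluable, and "The DLT window will start on day 1 and last for the duration of cycle 1".

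**Interim rule.** Protocol 9.4.1.1: "A DLRM will occur when at least 10 treated subjects in cohort 1 have been dosed through study day 28". Appendix 3 (11.3) and SAP 7.1 use the same trigger. The guidance is then not to initiate cohort 2 if 3 or more of the 10 treated subjects have a DLT by day 28. The basis is a posterior probability above 70% that the DLT rate exceeds 20%, with a Beta(0.40, 1.60) prior. Under 6.2.1 an individual's dosing stops at any DLT and may resume only after review.

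**The concern.** The authors saw that replacing a subject could remove a DLT from the stopping rule, and they closed that gap for the sentinel alone. For everyone else, the 10 in the rule can mean the first 10 treated or the 10 who reached day 28. On the second reading, a non-sentinel stopped in the lead-in drops out of both numerator and denominator and a new subject fills the place. That selects subjects on the outcome being counted and pushes the observed rate down.

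This is the only scheduled dose level review before cohort 2, where both drugs start on day 1. If lead-in DLTs leave the count, the gate stops less often than the stated probabilities say.

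**Working it through.** **1. Reproduce the plan's figures.** Inputs from 9.4.1.1: n = 10, cut-off 3, true rates of 10% to 50%. With X ~ Binomial(10, p):

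| True rate | Stated | P(X ≥ 3) | P(X ≥ 4) |
|---|---|---|---|
| 10% | 7% | 7.0% | 1.3% |
| 20% | 32% | 32.2% | 12.1% |
| 30% | 62% | 61.7% | 35.0% |
| 40% | 83% | 83.3% | 61.8% |
| 50% | 95% | 94.5% | 82.8% |

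The stated figures are those for 3 or more of 10, with p the full DLT rate by day 28. They assume that no DLT is removed.

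**2. Posterior at the boundary.** With x DLTs in n subjects the posterior is Beta(0.4 + x, 1.6 + n − x). P(rate > 20%) is:
- 3/10: Beta(3.4, 8.6), 0.72, above 0.70.
- 2/10: Beta(2.4, 9.6), 0.44, below 0.70.

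So if 3 of the first 10 have a DLT, one of them a non-sentinel on days 8–14 who is replaced uncounted by a subject without a DLT, 3/10 becomes 2/10 and the 9.4.1.1 guidance reverses.

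**3. Illustrative effect on the stopping probability.** The documents give no split of DLT risk by period, so these inputs are assumptions: 10% on days 1–14, 15% on days 15–28 among those who pass the lead-in, and a share s of the lead-in DLTs on days 8–14.
- Total by day 28: p = 1 − 0.90 × 0.85 = 0.235. If all count, P(X ≥ 3 | 10, 0.235) = 43%.
- Risk removed by replacement: q = 0.10 × s. The rate among subjects left in the count is r = (p − q)/(1 − q), and P(stop) = P(X ≥ 3 | 10, r).
- Keeping sentinel DLTs, with the role re-assigned after each: P(stop) = Σ over k ≥ 0 of q^k (1 − q) × P(X ≥ 3 − k | 10, r).

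| s | q | r | P(stop), no days 8–14 DLT counted | P(stop), sentinel's kept |
|---|---|---|---|---|
| 25% | 0.025 | 0.215 | 37% | 38% |
| 50% | 0.050 | 0.195 | 31% | 32% |
| 75% | 0.075 | 0.173 | 24% | 27% |

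**4. What happens if replaced subjects are kept and replacements added.** Then n exceeds 10. Three DLTs give 0.66 at n = 11 and 0.61 at n = 12, both below 0.70. A fixed cut-off of 3 no longer matches its stated basis, so settling the numerator alone is not enough.

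**The case against.** The best reply is that the rule already keeps these DLTs. The counting sentence in 9.4.1.1 speaks of treated subjects with a DLT by day 28, has no sentinel limit, and sits with a DLT window that opens on day 1. Dosing to day 28 fixes when the meeting happens; it is not written as the denominator. The stated probabilities match this reading, and no passage says that a replaced subject's DLT is excluded. All of this stands. It makes the loss possible rather than certain. It does not remove the ambiguity, because the sentinel-only sentence in 6.2.1 would be needless if the rule spoke for itself, and the interim rule does not refer to the DLT-evaluable set.

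A reader might infer that being replaced and being DLT evaluable contradict each other. They need not: 4.2.1 has a second backfill target (10 dosed to day 28), and a subject stopped before pembrolizumab can be evaluable yet give no combination exposure.

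A reader might also drop every lead-in DLT and get P(X ≥ 3 | 10, 0.15) = 18%. The replacement text does not support that. It covers the 7 days at one step, not days 1–14, and the sentinel's DLT is kept.

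Nor does 2/10 open cohort 2 automatically. The cut-off is guidance to the dose level review team, which sees all available data and must vote unanimously to escalate; the sponsor then decides.

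**Conclusion.** The point holds as an ambiguity in the interim rule: the documents do not settle whether a replaced non-sentinel's lead-in DLT counts, they use different lead-in windows, and they leave the denominator open. They do not support the stronger inference that such DLTs are excluded, or that the cohort 2 decision is necessarily biased.

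One lost DLT is enough to reverse the 9.4.1.1 guidance at the boundary (0.72 to 0.44). The fall from 43% to about 37–24% (38–27% with the sentinel's DLT kept) rests on assumed period risks and an assumed share on days 8–14, and is illustrative only. The final DLT table is unaffected, because it uses the DLT-evaluable set and any subject with a DLT belongs to it.

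**What to change.** Reconcile Protocol 4.1.1, 4.2.1, 6.2.1 and 9.4.1.1 (with the matching trigger in 11.3) and SAP 3.1.1 and 7.1:

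1. State that every treated cohort 1 subject with a DLT by day 28, sentinel or not and replaced or not, counts in the numerator and denominator of the interim rule.
2. Use one definition of the lead-in window throughout.
3. Define the denominator in one of two ways:
   - The first 10 treated subjects, each followed to day 28 or to a DLT. The stated probabilities then stand. Say how a DLT in a later, backfilled subject is handled.
   - All treated subjects at the review, with the stated posterior criterion (above 70% that the rate exceeds 20%) applied at the actual n in place of a fixed cut-off of 3. The stopping probabilities must then be recalculated.

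Separately, Protocol 4.1 and 6.2.1 and SAP 3.1 let cohort 2 proceed at up to and including 3 of 10, while Protocol 9.4.1.1 and SAP 7.1 advise against it at 3 or more. At exactly 3 of 10 they conflict, and these passages must be reconciled.

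The cost is wording in both documents, plus a short boundary table and recalculation under the second option. No extra subjects or data are needed.
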